4.8 Screen failure procedures

Subjects will be screened initially by phone or in person interview. If they are not eligible to continue, they will not be scheduled for a laboratory session. Those who pass the pre-screening will be scheduled to come to the laboratory for session 1. The subject will complete the baseline questionnaires that will

be reviewed to verify the subject continues to meet the inclusion and exclusion criteria. If this screening detects an issue, the subject will not continue with the study.

5 STUDY EVALUATIONS AND MEASUREMENTS (how measurements will be made)

All data will be collected from subjects in the laboratory setting.

Pain numeric rating scale for current pain and pain over the past week

The intensity of any current knee pain and average knee pain over the past week will be rated using the Numeric Pain Rating Scale (NPRS) (Huskisson 1974). Pain is marked on the scale from 0 mm representing “no pain” to 100 mm representing “maximal pain.” The NPRS has moderate to good reliability (ICC= .71-99) and for measuring musculoskeletal pain (Good, Stiller et al. 2001; Kahl and Cleland 2005) and a MCID of 18 mm in individuals with knee osteoarthritis (Singh, Luo et al. 2014).

Pain Catastrophizing Scale

The PCS is a 13-item questionnaire to quantify pain catastrophizing, a maladaptive cognitive style of coping with pain that includes the tendency to magnify the threat of pain, to feel helpless in the context of pain, and to ruminate (Sullivan 1995; Quartana, Campbell et al. 2009). Items are rated, based on the degree that the person has thoughts or feelings when experiencing pain, from 0 “not at all” to 4 “all the time”. The range for the total score is from 0 to 52 with higher scores associated with higher pain catastrophizing. The PCS components and total score have been shown to have acceptable reliability ($\alpha= .74\text{-.91}$) and validity in both clinical and non-clinical populations (Osman, Barrios et al. 1997; Van Damme, Crombez et al. 2002; George, Valencia et al. 2010). In people with knee OA, a PCS cutoff score of 16 or higher before surgery predicted poor outcomes after knee arthroplasty (Riddle, Wade et al. 2010).

UCLA Activity Score

The participant rates their level of physical activity. The range is from 1, defined as “no physical activity, dependent on others” to 10, defined as ““regular participation in impact sports.” It has been shown to have construct validity for monitoring physical activity with knee OA (Terwee, Bouwmeester, et al 2011).

Western Ontario and McMaster Universities Arthritis Index (WOMAC)

The Western Ontario and McMaster Universities Osteoarthritis Index (WOMAC) (Bellamy, Buchanan et al. 1988) (Hawker, Wright et al. 2001) (Mahomed, Liang et al. 2002) (Hawker, Wright et al. 1998) (Bullens, van Loon et al. 2001) is one of the most commonly used patient-reported outcome measures for knee OA, provides ratings of pain severity during various positions or movements, severity of joint stiffness, and difficulty performing daily functional activities (Collins, Misra et al. 2011). Each item is scored from 0 to 4 with higher scores indicating worse pain, stiffness, or physical function. The total score for each subscale is determined by adding the items. A total score from 0 (no problems) to 96 (extreme problems) can be calculated. The WOMAC has moderate to good reliability for the three subscales (ICC $> .75$) (Gandek 2015) and an MCID of 4-9 points (Williams, Piva et al. 2012).

Vital Signs

The participant's blood pressure and pulse will be taken prior to data collection. Fainting due to a sudden drop in blood pressure is called syncope. Syncope with TMS and rTMS is rare and occurs at a rate similar to other medical procedures such as drawing blood. However, anyone with low blood pressure (< 90 systolic and < 60 diastolic) or slow heart rate (< 50 beats per minute) or feeling light headed will be excluded. In our intake Knee History Questionnaire, the participant is asked about their sleep in the past 24 hours to determine if he/she may be sleep deprived.

How many hours of sleep did you get last night? _____ Is this normal for you? ? No ? Yes

If the subject reports less than 7 hours of sleep we further explore the sleep pattern. We will ask the participant if this is a normal amount of sleep for him/her and if he/she had a nap in the past 24 hours. If the total reported amount of sleep is off by 2 hours or more compared to their normal pattern, we will consider this a sign of sleep deprivation and the subject will be rescheduled for another time.

Timed-Up-And-Go Test (TUG)

The Timed-Up-And-Go Test is a measure of function, balance, and walking ability. Participants will be seated in a standard chair with arm rests and instructed to complete the test and quickly and as safely as possible.

Instructions will be to rise from the chair, walk to a line 3 m away, turn, walk back to the chair and return to a sitting position in the chair. Time to complete the task will be measured using a stop watch and recorded. The test will be repeated 3 times and the Timed-Up-And-Go scores will be averaged.

Pressure Pain Threshold (PPT)

Pressure Pain Threshold is a quantitative sensory test. The device is pressed on the skin with increasing amount of pressure until the subject indicates the stimulus is painful. It will be measured using the AlgoMed Computerized Pressure Algometer. Pressure Pain Threshold will be determined at 4 sites for the leg of the symptomatic and asymptomatic knee. The sites are: knee medial joint line, knee lateral joint line, 12 cm distal to knee lateral joint line (area of tibialis anterior muscle) and the ipsilateral heel plantar surface. We will also measure 1 site at the lateral elbow, bilaterally. Each site will be marked using an indelible marker. Each location will be measured 3 times each site. The tip of the pressure algometer will be applied with increasing pressure until the participant indicates a change from a pressure sensation to a painful sensation. Pressure Pain Threshold will be the average of 3 trials for each location.

Quadriceps Function: Strength (MVIC), Central Activation Ratio (CAR), Superimposed Torque (ST)

We will follow the same procedures for the symptomatic and asymptomatic knee. We will be following a well established protocol that has been used in many studies within the UNC Neuromuscular and Sports Medicine Research Laboratories (Luc et al, 2016, [name] et al, 2015, Lepley et al, 2015). Participants will be seated on a device used to measure muscle strength called an isokinetic dynamometer (Humac). Straps will be used to secure the torso, thigh, and lower leg to the device with the knee in 70° of flexion. The moveable arm of the dynamometer will be fixed in place because we are taking measurements of quadriceps strength when the muscle is performing an isometric contraction. An isometric contraction means that the leg does not move.

Participants will be asked to contract the quadriceps maximally and as quickly as possible by “kicking out” against the dynamometer in response to a verbal cue while torque data are sampled. This represents the quadriceps maximal voluntary isometric contraction (MVIC). To calculate the capacity of the anterior thigh muscle (quadriceps) to produce more torque (force times distance), we will have electrodes placed on the thigh muscle and apply a brief intense electrical stimulus to a maximally contracting muscle (superimposed burst of electrical stimulation), which activates all the muscle’s motor units in the area. This produces a measurement we call the superimposed torque (ST), which is the voluntary strength plus more elicited with the strong electrical stimulus. The torque resulting from the superimposed burst of electrical stimulation (ST) and the maximal voluntary isometric contraction (MVIC) are used to calculate the level of quadriceps voluntary activation as a percentage, referred to as the Central Activation Ratio (CAR). People without knee problems may produce a CAR from the thigh muscle of about 95%, whereas people with knee arthritis may produce only 80% to 90%. Participants will perform 3 to 5 practice trials to become familiar and comfortable with these procedures. Three trials will then be recorded from which the measurements will be averaged for statistical analyses.

A Grass electrical stimulator is used to create the brief intense electrical stimulation to the anterior thigh muscle. The Grass stimulator consists of two parts: the S48 Stimulator and SIU8T isolation units. Both the S48 Stimulator and SIU8T isolation units meet the follow safety standards: UL 3101-1, CSA C22.2 No. 1010-1, EN 61010-1. In this study, we are not assessing the clinical safety or efficacy of the Grass stimulator. We are using the Grass stimulator to measure a physiological principle, which is the level of voluntary activation of the quadriceps muscle. Therefore, the use of the Grass stimulator for quantification of voluntary activation is defined as non-invasive as well as a non-significant risk device under the FDA Code of Federal Regulations, Title 21, Section 812.3.

Additionally, the Grass stimulator was approved by UNC Health and Safety on January 26, 2015. [name] from Health and Safety inspected the Grass and cleared it for use. (see IRB# 15-1150) The Grass stimulator will be isolated from fluctuations in building’s electrical power supply via a stimulus isolation unit. The Grass stimulator, methods, and stimulus characteristics have been was approved for use in other investigations (conducted on subjects with knee OA and healthy controls) in the UNC Neuromuscular and Sports Medicine Research Laboratories., IRB# 12-0189).

Neural Excitability (Motor Cortex and SubMotor Cortex): Measurements from Transcranial Magnetic Stimulation (TMS), Single-pulse and Double-pulse Stimuli

We will follow the same procedures for the symptomatic and asymptomatic knee. The TMS stimulus is produced and controlled with the Magstim BiStim Unit. The stimulation intensity can be increased or decreased by turning a dial on the unit. When one stimulus is sent by this TMS unit to the stimulating coil, this is referred to as single-pulse TMS. Measurements made using single-pulse TMS represents the excitability of both the brain (cortex) and subcortical regions of the central nervous system (Rossini, 2015). Recording electrodes placed over the belly of a muscle, referred to as electromyography, shows the outcome of the TMS stimulus when the appropriate motor area of the brain is stimulated. The muscle’s motor threshold is the defined as the lowest single-pulse TMS intensity that elicits motor evoked potentials (MEPs) from the muscle in 50% of trials (George and

Belmaker, 2007). If the muscle is active during the test, it is referred to as the active motor threshold (AMT), which is defined as the stimulus required to elicit a peak-to-peak amplitude of $>100 \mu\text{V}$ with the muscle activated (George and Belmaker, 2007). We will obtain measurements of active motor threshold motor evoked potentials (AMT-MEP) from the anterior thigh muscle from both the symptomatic and asymptomatic knee in Session 1. In Sessions 2 and 3, these measurements will be made before and after the intervention and only from the symptomatic knee.

The above single-pulse TMS measurements have been obtained using the Magstim BiStim unit in previous investigations in the Neuromuscular and Sports Medicine Research Laboratories. The procedures have been implemented with no adverse events (IRB #15-1345, IRB #14-1978, IRB #13-2314, IRB #13-3228). The results have been disseminated in peer reviewed literature (Gibbons et al, 2010; [name] et al, 2015; Luc et al, 2014; Thomas et al, 2015).

The subject will be prepared for the TMS testing by placing a lycra swim cap with a 20 cm x 20 cm grid on the head to locate the optimal area of stimulation for the quadriceps. The lycra swim caps used can be washed following each session. Perpendicular lines from the bridge of the nose to the center of the back of the head (occiput) and from ear (external auditory meatus) to ear will be measured to ensure the cap is centered and placed in the same location for each testing session. The perpendicular lines also serve as a coordinate system for the grid, to better identify the optimal “hot spot” in the motor area of the brain for TMS stimulation of the anterior thigh muscle.

For all TMS testing, participants will be instructed to sit and relax and to focus on the computer screen in front of them depicting the force produced by their quadriceps. Participants will be instructed to clear their mind of any additional thoughts and to remain awake and alert to control for mental-state variability throughout testing.

We will use the Magstim Bistim unit to establish the active motor threshold (AMT). During this test, the participant will be instructed to contract their thigh muscle to 5% of their previously measured maximum (MVIC). The level of torque to achieve 5% maximum will be depicted by a line on the computer screen in front of them. The magnitude of the active motor threshold (AMT) will be determined by muscle responses (motor evoked potentials) that are $>100 \mu\text{V}$ (peak-to-peak). Participants will wear a Lycra swim cap with two perpendicular lines that intersected at the vertex of the cranium, thus sectioning the head into quadrants (11). The swim cap is positioned such that one line connected the center of the occiput and nose, and the second line connected the left and right external auditory meatus (11). The quadrants posterior to the intersection of the two lines denoted the approximate location of the motor cortex (11). A 11 x 8 cm grid consisting of points located 1 cm apart is drawn on the posterior quadrants of swim cap in to allow for movement of the coil in a systematic pattern to locate the optimal point to apply TMS. Initial stimuli are provided at 60% of the maximum stimulator output to locate the optimum coil placement to elicit maximal motor evoked potentials (MEPs). Two stimuli are delivered at each grid location of the swim cap. After systematically stimulating the points on the motor cortex, contralateral to the limb being tested, the grid location producing the greatest MEP amplitude is determined to be the “hot spot” and is marked on the swim cap for subsequent testing (14). The orientation of the coil is traced on

the swim cap in order to ensure exact placement and positioning of the coil each time a stimulus is delivered. AMT is defined as the lowest TMS intensity required to evoke a measurable MEP (>100 μ V) in 5 out of 10 consecutive measurements (15). Once 5 out of 10 measurable MEPs are elicited, the intensity level will be decreased by 1% until a total of 6 out of 10 stimuli fail to elicit an MEP amplitude greater than 100 μ V (15). The peak-to-peak amplitude of the signals from the thigh muscle will be measured and averaged for the AMT-MEP outcome variable.

After the AMT-MEP is established, 10 stimuli are first delivered at a stimulus intensity of 120% of AMT in order to normalize the MEPs elicited via paired pulse paradigms; paired-pulse paradigms were completed immediately after establishing the normal magnitude of MEPs elicited at 120% of AMT. These 120% AMT measurements are needed for assessing motor cortex inhibition and facilitation. The order of the paired pulse paradigms (intracortical inhibition (SICI) or intracortical facilitation (ICF)) will be randomized and determined once a participant is enrolled into the study.

For ICF, a conditioning stimulus was applied at 80% of AMT 15 ms prior to the testing stimulus, which was applied at 120% of AMT (16). For SICI the conditioning stimulus was applied at 80% of AMT 3 ms prior to the testing stimulus, which was applied at 120% of AMT (16). 10 stimuli were delivered for both SICI and ICF. AMT, SICI, and ICF are reliable measures of corticospinal and intracortical excitability (17, 18). Peak-to-peak MEP amplitudes were measured and recorded for each testing paradigm (120% of AMT, SICI and ICF), and the 10 MEP amplitudes elicited from each testing paradigm were averaged within each participant. Average MEP amplitudes elicited via SICI and ICF paradigms were then normalized to the average MEP amplitude elicited at 120% of AMT for each participant. A lesser conditioned response, or lesser amplitude elicited via the SICI paradigm indicates greater intracortical inhibition, whereas a greater conditioned response, or greater amplitude elicited via the ICF paradigm indicates greater intracortical facilitation.

- 5.1 Efficacy Evaluation (if applicable)** NA
- 5.2 Pharmacokinetic Evaluation (if applicable)** NA
- 5.3 Safety Evaluations**

We will describe any potential physical risks, including the category of likelihood and severity, and what will be done to minimize these risks. We describe the likelihood of the risks occurring, using the following terms:

- Very Common (approximate incidence > 50%)
- Common (approximate incidence > 25 - 50%)
- Likely (approximate incidence of > 10 - 25%)
- Infrequent (approximate incidence of > 1 - 10%)
- Rare (approximate incidence < 1%)

We Describe severity of risks using the following grading scale:

- Mild- No disruption to the subject's ability to perform daily activities; may include non-prescription intervention only
- Moderate- Temporary interference with daily activities; may include prescription intervention
- Severe- Interference with daily activities; medically significant but not life threatening
- Life threatening

Very common: The electrical stimulation used during the Quadriceps Voluntary Activation assessment, though extremely brief (less than 1/1000 of a second), may commonly cause discomfort – not pain – during testing.

Likely: The noise from the rTMS device will likely be uncomfortable to the subjects. Humans exposed to TMS have shown temporary increases in auditory threshold (especially at high frequencies) lasting at least 5 minutes and less than 4 hours. We will provide earplugs to reduce the noise level.

Infrequent: Muscle soreness and knee joint soreness from contracting the quadriceps may occur, but will be minimal and the soreness should go away within a day. The thigh muscle contractions during the muscle strength testing may infrequently result in muscle soreness or, in extremely rare cases, muscle injury. Participants will be provided with warm-up exercise before completing these tasks and provided adequate rest breaks between tasks in order to reduce the risk of injury.

Some people report mild discomfort when the TMS pulses are applied over the scalp. A small number of people (~5%) report headache following rTMS. However, the headaches are temporary and manageable with common over-the-counter pain remedies.

Rare: There is a possibility of discomfort associated with prepping the areas where electromyographic (EMG) sensors will be placed (i.e. shaved, lightly abraded, and cleaned with alcohol).

Syncpe is defined as a momentary loss of awareness and postural tone. It typically has a rapid onset, short duration, and spontaneous recovery. Although syncopal episodes are very rare with TMS (less than 1%), they typically occur during the motor threshold procedure before the rTMS treatment has begun. Individuals that are sleep deprived and have low or unstable blood pressure are at greater risk. The participant's blood pressure and pulse will be taken prior to data collection. Fainting due to a sudden drop in blood pressure is called syncpe. Syncpe with TMS and rTMS is rare and occurs at a rate similar to other medical procedures such as drawing blood. However, anyone with low blood pressure (< 90 systolic and < 60 diastolic) or slow heart rate (< 50 beats per minute) or feeling light headed will be excluded from continuing on to the TMS testing.

Regarding sleep deprivation, in our intake Knee History Questionnaire, the participant is asked about their sleep in the past 24 hours to determine if he/she may be sleep deprived. The questions specifically are:

How many hours of sleep did you get last night? _____ Is this normal for you? No Yes

If the subject reports less than 7 hours of sleep we further explore the sleep pattern. We will ask the participant if this is a normal amount of sleep for him/her and if he/she had a nap in the past 24 hours. If the total reported amount of sleep is off by 2 hours or more compared to their normal pattern, we will consider this a sign of sleep deprivation and the subject will be rescheduled to return for testing on another day.

There is a very rare risk of seizure. TMS stimulates the neurons in the brain at a level below what is required to cause a seizure, although eight seizures have been noted in the literature in the past 20 years. Six of them have been in healthy volunteers (without any history of seizures, brain masses or traumatic brain injuries). The risk of seizure induction is related to the intensity, duration, frequency and rest interval of stimulation. Following the adoption and widespread use of the safety guidelines, 1 seizure has been reported since 1997 and it involved parameters of higher settings than the safe range (Rossi, 2009). The stimulation with the parameters and settings we propose to use are adjusted to the participant's motor threshold and we have included a long "on" to "off" ratio during the repetitive TMS intervention. Our ratio of 1:11 well exceeds the safety guideline of 1:2. To be safe, we have excluded

individuals with a history of seizures or epilepsy. We have also excluded people with a history of head injury and medications that could lower the seizure threshold. By following all of the published safety guidelines, the risk of seizure is rare.

There are always possibilities that unknown side effects may occur during or following testing.

Participants will be monitored throughout the study for any adverse events and will be withdrawn from the study if they report any adverse events associated with either the testing or the intervention. In the event that a participant sustains an injury during the study, they will be referred to the appropriate medical personnel on campus (i.e. Campus Health Services or the UNC Hospitals Emergency Room).

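### The single-pulse TMS outcome (AMT-MEP) reads as an amplitude taken at each limb's own threshold, so it would barely register a between-limb threshold difference, and the Aim 1 analysis does not commit to threshold intensity

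*Combined protocol and SAP*

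**What the plan says.** Section 2.2 sets the secondary objective: compare motor cortex and corticospinal excitability between the two knees, and relate it to pain, strength, function and coping style.

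Section 5 (Neural Excitability) describes the measurement.

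- Both limbs are tested alike: "We will follow the same procedures for the symptomatic and asymptomatic knee". The Session 1 single-pulse measurement is named: "We will obtain measurements of active motor threshold motor evoked potentials (AMT-MEP) from the anterior thigh muscle from both the symptomatic and asymptomatic knee". That sentence does not say whether AMT-MEP is an amplitude or an intensity.
- AMT is an intensity, the lowest that gives a response above 100 microvolts in 5 of 10 stimuli. From there "the intensity level will be decreased by 1% until a total of 6 out of 10 stimuli fail to elicit an MEP amplitude" above the criterion.
- Directly after this search comes the outcome definition: "The peak-to-peak amplitude of the signals from the thigh muscle will be measured and averaged for the AMT-MEP outcome variable". It states no intensity and no number of stimuli.
- The next step is: "After the AMT-MEP is established, 10 stimuli are first delivered at a stimulus intensity of 120% of AMT". Its purpose is also given: "These 120% AMT measurements are needed for assessing motor cortex inhibition and facilitation".
- The same part says: "AMT, SICI, and ICF are reliable measures of corticospinal and intracortical excitability".

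Section 6.3 and the SAP's Statistical Methods refer to excitability measures only as a group. They name none of AMT, AMT-MEP, SICI or ICF. Section 4.2 lists AMT-MEP, SICI and ICF, but for Sessions 2 and 3 only, so its silence on AMT says nothing about Aim 1.

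**The concern.** A threshold search changes the stimulus until the response reaches a fixed size. Its result is the intensity that was needed. The size of the response at the end of the search is set by the stopping rule. A limb with lower corticospinal excitability needs more stimulator output to reach 100 microvolts, so its AMT is higher while its response is about the same size as in the other limb.

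If the amplitude is what gets compared and correlated, the single-pulse part of Aim 1 carries almost no information about threshold. A null result could then be taken as no corticospinal difference when the measure could hardly have shown one. SICI and ICF still cover the intracortical part of the objective.

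**Working it through.** **Which stimuli are averaged?** The documents state no figure for any TMS measure (Section 6.4 covers MVIC and CAR only), so this starts from the text.

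- For the limb's own threshold: the name AMT-MEP, the position of the sentence straight after the search, and the fact that the 120% stimuli come only once AMT-MEP is established. The 120% amplitude is therefore a different quantity. It is also scaled to the limb's own AMT, so it is no substitute.
- For a loose label meaning the threshold itself: Section 4.2 has the trio AMT-MEP, SICI, ICF, while Section 5 has AMT, SICI, ICF.
- A fixed intensity also appears: "Initial stimuli are provided at 60% of the maximum stimulator output to locate the optimum coil placement". It is given for locating the hot spot, not for the threshold search.

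**Assumed inputs.** All physiological values are assumptions.

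- Median response at intensity I for a limb with threshold T: 100 × exp(g × (I − T)) microvolts, with log-normal trial-to-trial variation of log-SD s.
- g = 0.06, 0.12 or 0.20 per 1% of output; s = 0.3, 0.6 or 0.8. Both also vary at random between limbs (log-SD 0.3).
- Base threshold 42 (SD 6) and SD of the between-limb difference 6, in points of output.
- 20 pairs (the planned N), paired t-test, two-sided 0.05.
- Search: start 10 points above T, 10 stimuli per step, 1% steps down, stop when 6 of 10 fail. AMT is the last intensity with at least 5 of 10 above 100 microvolts. AMT-MEP is the mean amplitude of that block.

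**Step 1: why the amplitude does not move.** At I = T the median is 100 × exp(0) = 100 microvolts whatever T is. A separate simulation (g 0.05 to 0.20) moved T from 40 to 48. Measured AMT rose by about 8 points. Mean AMT-MEP stayed at about 114-117 microvolts for s = 0.3, 131-134 for s = 0.5 and 155-166 for s = 0.7. By contrast, amplitude at any fixed intensity falls by 1 − exp(−8g): 33%, 55% and 80% for g = 0.05, 0.10 and 0.20.

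**Step 2: limb comparison.** With AMT measured without error, the noncentrality is √20 × difference / 6, which is 1.49, 2.24 and 3.73 for 2, 3 and 5 points. Paired-t power is then 29%, 56% and 94%. Error in the search lowers this a little:

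| Mean threshold difference | AMT rejects | AMT-MEP rejects |
|---|---|---|
| 2 points | about 18-28% | about 3-7% |
| 3 points | about 35-55% | about 3-7% |
| 5 points | about 80-94% | about 3-7% |

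Averaging the stopping block instead gives the same picture (3-7% at 5 points).

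**Step 3: correlations.** With a true correlation of 0.6 between threshold and a clinical score, n = 20, the mean Spearman coefficient is about 0.48-0.55 with AMT and about 0 with AMT-MEP.

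**Step 4: unequal variability (secondary caution).** At threshold the mean amplitude is 100 × exp(s²/2): 108 microvolts for s = 0.4 and 128 for s = 0.7. The search rule widens the gap. With no mean threshold difference and the same random variation between limbs, AMT-MEP on the raw scale rejects in about 67-78% for 0.4 versus 0.7, and in about 11-14% for 0.5 versus 0.6.

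**Step 5: a reading that would respond.** Averaging every stimulus of a search started at a fixed 60% of output gives 37-79% rejection at 5 points, with g and s held constant.

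**The case against.** The strongest reply is that this is an unclear label and not a settled choice. Only one sentence makes AMT-MEP an amplitude, and the two trios suggest that the authors may mean the threshold. Section 5 calls AMT a reliable excitability measure, and the Aim 1 analysis covers excitability measures in general, so AMT can fall within it. AMT must be known for each limb anyway, to set the 80% and 120% stimuli.

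Much of this stands. A reader might infer that the plan leaves AMT out, or that Aim 1 cannot detect a corticospinal difference. The documents support neither: they permit an AMT analysis, and no section says that a null AMT-MEP result would be read as no difference. What remains is that the only sentence defining the outcome makes it an amplitude, and that no section commits to comparing AMT intensity.

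Two further points are fair. The flat response of AMT-MEP is built into the model, but it is built into the stopping rule in the same way, and the assumptions affect only the size. The advantage of AMT depends on the true difference and is modest at 2 points. A reader might also infer that unequal variability will produce false positives. The documents do not suggest that variability differs between limbs.

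**Conclusion.** The point holds on the natural reading of Section 5, with medium confidence because the averaged stimuli are not stated. On that reading AMT-MEP rejects at about 3-7%, close to the nominal 5%, whatever the threshold difference. AMT intensity responds, from about 18-28% at 2 points to 80-94% at 5 points. These sizes rest wholly on assumed recruitment slopes, trial noise and an SD of 6 points; the direction follows from the search rule. The warning about unequal variability is conditional and secondary.

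The reach is limited to the single-pulse outcome of the secondary, descriptive aim. MVIC, CAR and the sample size are unaffected. It should be corrected, because a named outcome that is nearly uninformative is more than a missing detail.

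**What to change.** - In Section 6.3 and the SAP's Statistical Methods, list AMT (% of stimulator output) as a corticospinal outcome for the Aim 1 limb comparison and correlations, beside SICI and ICF.
- In Section 5, state which stimuli, how many and at which intensity form AMT-MEP. If they are the threshold stimuli, AMT-MEP may be reported but should not be read as evidence for or against a corticospinal difference.
- In Section 4.2, state whether AMT is searched again at post-test in Sessions 2 and 3. If it is, analyse AMT before and after the intervention.

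The cost is a few sentences. No new data are needed, since AMT is already required at each measurement to set the paired-pulse stimuli.
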